**Clinical Study Protocol SMOF-028-CP4**  
**Smoflipid® (lipid injectable emulsion)**

---

**Clinical Study Protocol SMOF-028-CP4**  
**Smoflipid® (lipid injectable emulsion)**

---

**Study outline**

**Title:** Prospective, Randomized (1:1), Double-Blind, Parallel-Group, Active-Controlled, Multicenter Study to Compare Safety and Efficacy of Smoflipid® to Intralipid® 20% in Pediatric Patients of 3 Months to 16 Years of Age Requiring Parenteral Nutrition for at Least 90 Days and up to 1 Year.

**Authority**

**Identification no.:** IND 102,137

**Fresenius Kabi**

**Study Identifier:** SMOF-028-CP4

**Indication:** Smoflipid (lipid injectable emulsion) is indicated as a source of calories and essential fatty acids for parenteral nutrition when oral or enteral nutrition is not possible, insufficient, or contraindicated.

**Study Phase:** 4

**Objectives:** Evaluate the safety and efficacy of Smoflipid (lipid injectable emulsion) compared to standard of care lipid emulsion Intralipid 20% (a 20% I.V. fat emulsion) administered via a central vein in pediatric patients 3 months to 16 years of age who require parenteral nutrition for at least 90 days and up to 1 year.

**Study Hypothesis:** Smoflipid (lipid injectable emulsion) is safe and effective in pediatric patients when administered for 90 days or up to 1 year.

**Study Drugs:** Investigational drug: Smoflipid (lipid injectable emulsion), referred to as Smoflipid in the following text.

Control drug: Intralipid 20% (a 20% I.V. fat emulsion), referred to as Intralipid 20% in the following text.

**Dosage of Study Drugs:** Dosage of Smoflipid and Intralipid 20%  
The dosing of the study drugs depends on the patient's individual energy requirements, age, body weight, tolerance, clinical status, and the ability to eliminate and metabolize lipids. A titration phase is necessary in patients with a new indication for PN treatment. Age groups are classified according to ICH (ICH 2000).

**Clinical Study Protocol SMOF-028-CP4**  
**Smoflipid® (lipid injectable emulsion)**

---

Study drugs will be started and advanced according to ASPEN pediatric nutrition recommendations (A.S.P.E.N. 2015) and center standards. Maximum dosage is according to the US Prescribing Information for Intralipid 20%, i.e., for pediatric patients up to 3 g/kg/d, and up to 2.5 g/kg/d for adolescents according to maximum dosage for adults.

A) Patients who start PN:

Infants 3 months to < 2 year of age:

start	0.5 to 1 g/kg/d lipid
advanced by	0.5 to 1 g/kg/d lipid
maximum	up to 3 g/kg/d lipid

Children 2 to < 12 years of age:

start	1 to 2 g/kg/d lipid
advanced by	0.5 to 1 g/kg/d lipid
maximum	up to 3 g/kg/d lipid

Adolescents 12 to 16 years of age:

start	1 g/kg/d lipid
advanced by	1 g/kg/d lipid
maximum	up to 2.5 g/kg/d lipid

B) Patients who already receive PN:

Infants 3 months to < 2 years of age:

up to 3 g/kg/d lipid

Children 2 to < 12 years of age:

up to 3 g/kg/d lipid

Adolescents 12 to 16 years of age:

Up to 2.5 g/kg/d lipid

Study drugs will be dosed at a weight-based infusion rate according to each patient's lipid needs and clinical condition. Investigational and control drug should be infused at constant rate for 10 to 24 h/d. Infusions should be given 5 to 7 days per week. Maximum infusion rate should not exceed 0.125 g/kg/h lipid.

Serum triglycerides and direct bilirubin will be monitored monthly to monitor lipid administration (see below, Study Treatment, Intravenous lipid dose management).

## Clinical Study Protocol SMOF-028-CP4 Smoflipid® (lipid injectable emulsion)

---

**Route of Administration:** The study drugs will be infused into a central vein via central venous catheter or peripherally inserted central catheter.

### Dosage of Other PN Components:

For total PN, amino acids, dextrose, electrolytes and micronutrients will be administered according to center standards taking into account the ASPEN recommendations for PN in pediatric patients (A.S.P.E.N. 2015). Age groups are classified according to ICH (ICH 2000). Energy needs will be estimated using equations for calculation (A.S.P.E.N. 2015).

The following dosages for amino acids and dextrose are recommended in the age groups. Dosage of dextrose will be adjusted to reach the target parenteral calories taking into account the calories from prescribed lipids and amino acids.

A) Patients who start PN:

#### Infants 3 months to < 2 years of age:

##### *Age 3 months to < 1 year*

- Amino Acids:    start           2.5 to 3 g/kg/d  
                          goal           2.5 to 3 g/kg/d
  
- Dextrose:       start           6 to 8 mg/kg/min  
  (8.6 to 11.5 g/kg/d)  
                          advanced by 3.5 mg/kg/min  
  (5 g/kg/d)  
                          maximum       14 to 18 mg/kg/min  
  (20.2 to 25.9 g/kg/d)

##### *Age 1 year to < 2 years:*

- Amino Acids:    start           1.5 to 2.5 g/kg/d  
                          goal           1.5 to 2.5 g/kg/d
  
- Dextrose:       start           3 to 6 mg/kg/min  
  (4.3 to 8.6 g/kg/d)  
                          advanced by 2 to 3 mg/kg/min  
  (2.9 to 4.3 g/kg/d)  
                          maximum       8 to 10 mg/kg/min  
  (11.5 to 14.4 g/kg/d)

#### Children 2 to < 12 years of age:

- Amino Acids:    start           1.5 to 2.5 g/kg/d  
                          goal           1.5 to 2.5 g/kg/d

## Clinical Study Protocol SMOF-028-CP4 Smoflipid® (lipid injectable emulsion)

---

- Dextrose: start 3 to 6 mg/kg/min  
(4.3 to 8.6 g/kg/d)  
advanced by 2 to 3 mg/kg/min  
(2.9 to 4.3 g/kg/d)  
maximum 8 to 10 mg/kg/min  
(11.5 to 14.4 g/kg/d)

### Adolescents 12 to 16 years of age:

- Amino Acids: start 0.8 to 2 g/kg/d  
goal 0.8 to 2 g/kg/d
- Dextrose: start 2.5 to 3 mg/kg/min  
(3.6 to 4.3 g/kg/d)  
advanced by 1 to 2 mg/kg/min  
(1.4 to 2.9 g/kg/d)  
maximum 5 to 6 mg/kg/min  
(7.2 to 8.6 g/kg/d)

### B) Patients who already receive PN:

#### Infants 3 months to < 2 year of age:

##### *Age 3 months to < 1 year*

- Amino Acids: goal 2.5 to 3 g/kg/d
- Dextrose maximum 14 to 18 mg/kg/min  
(20.2 to 25.9 g/kg/d)

##### *Age 1 to < 2 years*

- Amino Acids: goal 1.5 to 2.5 g/kg/d
- Dextrose: maximum 8 to 10 mg/kg/min  
(11.5 to 14.4 g/kg/d)

#### Children 2 to < 12 years of age:

- Amino Acids: goal 1.5 to 2.5 g/kg/d
- Dextrose: maximum 8 to 10 mg/kg/min  
(11.5 to 14.4 g/kg/d)

#### Adolescents 12 to 16 years of age:

- Amino Acids: goal 0.8 to 2 g/kg/d
- Dextrose: maximum 5 to 6 mg/kg/min  
(7.2 to 8.6 g/kg/d)

Other parenteral nutrients (e.g., L-cysteine hydrochloride, carnitine) will be administered according to hospital practice and applicable guidelines (A.S.P.E.N. 2015).

## Clinical Study Protocol SMOF-028-CP4 Smoflipid® (lipid injectable emulsion)

---

**Oral or Enteral Nutrition:** Patients are included if 60% or more of their calorie needs are provided by PN (see below, Inclusion Criteria). If a patient can partially be nourished orally or enterally, the energy intake will be calculated and the dosage of PN will be reduced correspondingly.

**Study Treatment:** Patients will be randomized 1:1 to receive either Smoflipid (investigational group) or Intralipid 20% (control group).

The blinded study drugs will be administered simultaneously with the other prescribed PN components. The patients will receive the study drugs according to their individual prescription on 5 to 7 days per week. Parenteral nutrition can be administered overnight (as usual in home care patients) or continuously over 10-24 h/day (mainly in hospital setting). The maximum infusion rate for the study drug must not be exceeded.

During the course of the study, dosage reductions of the study drug can be necessary as consequence of laboratory analyses. Serum triglyceride (TG) levels should be kept < 250 mg/dL throughout treatment with a study drug. If higher levels develop, the dosage of the lipid emulsion will be reduced. Persisting higher levels can lead to the decision that a patient is removed from the study. Also, direct bilirubin levels in plasma will be used to decide about dosage reduction or cessation of the study drug infusions. The procedures will be as follows:

### Serum triglycerides for intravenous lipid dose management:

#### A) Patients who start PN:

During dose titration, levels of TG will be monitored daily. Should TG exceed 250 mg/dL, the study drug will be held until analysis of another blood sample on the following morning. If TG are  $\leq$  250 mg/dL the study drug is restarted. If not this procedure has to be repeated on each subsequent morning. If after 3 days TGs still exceed 250 mg/dL, the patient will be removed from the study.

Once the target dose has been reached at level of serum TG  $\leq$  250 mg/dL, TG will be assessed monthly.

B) Patients who already receive PN:

Triglycerides levels will be monitored monthly. Should TG exceed 250 mg/dL, a confirmatory analysis must be performed after 7 days. If the confirmatory analysis reveals that TG still exceed 250 mg/L, the study drug dosage should be reduced, or the patient should be removed from the study, at discretion of the Investigator.

Direct bilirubin for intravenous lipid dose management:

Direct bilirubin levels will be assessed monthly. If at any point direct bilirubin exceeds 2.0 mg/dL (> 2.0 mg/dL), a confirmatory analysis must be performed after 7 days. If the confirmatory analysis reveals that direct bilirubin is still > 2.0 mg/dL, the lipid dose has to be decreased to 1 g/kg/day; dextrose dose should be increased accordingly to maintain adequate energy provision. Lipid dose will be maintained at 1 g/kg/d and not be increased again even if direct bilirubin levels decrease again to 2.0 mg/dL or lower.

If at any point direct bilirubin exceeds 4 mg/dL (> 4 mg/dL), the patient must be taken off study treatment. In this case, further PN treatment is at the discretion of the Investigator.

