**Duration of Treatment:**

Study treatment will last for a minimum of 90 consecutive days and as long as PN is indicated, up to 365 consecutive days. The study ends after the Final Study Visit, latest on Day 366 (see Section 1, Study Schedule). If the indication for PN continues after Study Day 365, PN will continue per normal institution policy. Study drugs will no longer be used.

Early termination of study treatment (Before Study Day 91)

The study treatment will stop if infusion of the study drug cannot be continued because TG or direct bilirubin levels remain above the defined limits (see above, Intravenous lipid dose management) after reduction of the dosage.

The study treatment will also be stopped if the Holman Index of a patient (biochemical marker for essential fatty acid deficiency (EFAD)) reaches or exceeds 0.4 or if any clinical symptoms of EFAD appear or when the patient's growth is inadequate (drop of 1 in z-score in a time period of 2 consecutive months).

The study treatment will also stop if enteral food tolerance increases and in consequence, less than 60% of the patient's

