## Clinical Study Protocol SMOF-028-CP4 Smoflipid® (lipid injectable emulsion)

---

energy requirements are provided by PN for at least one month. If PN is still indicated after termination of the study treatment, it will continue per normal institution policy.

In case of early termination, patients will be replaced by randomizing additional patients unless the decision to terminate was made for safety reasons (including intravenous lipid dose management).

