## Clinical Study Protocol SMOF-028-CP4

### Smoflipid® (lipid injectable emulsion)

---

2. Hyperlipidemia or disorders of lipid metabolism characterized by hypertriglyceridemia (serum triglyceride concentration > 250 mg/dL).
3. Inborn errors of amino acid metabolism.
4. Cardiopulmonary instability (including pulmonary edema, cardiac insufficiency, myocardial infarction, acidosis and hemodynamic instability requiring significant vasopressor support).
5. Hemophagocytic syndrome.
6. Liver enzymes (either AST or ALT or GGT) exceeding 5 x upper limit of normal range
7. Direct bilirubin  $\geq$  2.0 mg/dL
8. INR > 2.
9. Any known hepatic condition outside of IFALD that will increase direct bilirubin levels  $\geq$  2.0 mg/dL .
10. Clinically significant abnormal levels of any serum electrolyte (sodium, potassium, magnesium, calcium, chloride, phosphate).
11. Active bloodstream infection demonstrated by positive blood culture at screening.
12. Severe renal failure including patients on renal replacement therapy.
13. Abnormal blood pH, oxygen saturation, or carbon dioxide.
14. Pregnancy or lactation.
15. Participation in another clinical study.
16. Unlikely to survive longer than 90 days.

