### 10.3.4 Intravenous Lipid Dose Management

Serum TG levels should be kept < 250 mg/dL throughout treatment with a study drug. If higher levels develop, the dosage of the lipid emulsion will be reduced. Persisting higher levels can lead to the decision that a patient is removed from the study. Also direct bilirubin levels in plasma will be used to decide about dosage reduction or cessation of the study drug infusions. Furthermore, cessation of study drug infusion will be obligatory in case EFAD or inadequate growth is observed.

The procedures will be as follows:

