#### Serum TG levels for intravenous lipid dose management:

##### A) Patients who start PN:

During dose titration, levels of TGs will be monitored daily. Should TGs exceed 250 mg/dL (> 250 mg/dL), the study drug will be held until analysis of another blood sample on the following morning. If TGs are ≤ 250 mg/dL the study drug is restarted. If not this procedure has to be repeated on each subsequent morning. If after 3 days TGs still exceed 250 mg/dL, the patient will be removed from the study.

Once the target dose has been reached at level of serum TG ≤ 250 mg/mL, TG levels will be assessed monthly.

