##### B) Patients who already receive PN:

Triglycerides levels will be monitored monthly. Should TGs exceed 250 mg/dL (> 250 mg/dL), a confirmatory analysis must be performed after 7 days. If the confirmatory analysis reveals that TGs still exceed 250 mg/L (> 250 mg/dL), the study drug dosage should be reduced, or the patient should be removed from the study, at discretion of the Investigator.

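### The confirmatory triglyceride limit for patients already on PN is printed as 250 mg/L (25 mg/dL), ten times below the 250 mg/dL used for the first test, the general limit and the exclusion criterion.

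*Combined protocol and SAP*

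**What the plan says.** The Study outline (Study Treatment, serum triglycerides for lipid dose management, part B) covers patients who already receive PN. The monthly test comes first: "Should TG exceed 250 mg/dL, a confirmatory analysis must be performed after 7 days". The sentence on the repeat test follows: "If the confirmatory analysis reveals that TG still exceed 250 mg/L, the study drug dosage should be reduced". The alternative to dose reduction is removal from the study, at the Investigator's discretion. Nothing in the outline corrects the unit.

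Section 10.3.4, part B, gives the same rule with two units in one sentence: "TGs still exceed 250 mg/L (> 250 mg/dL), the study drug dosage should be reduced".

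The other limits that bear on this rule are in mg/dL. Section 10.3.4 opens with the general limit, "Serum TG levels should be kept < 250 mg/dL throughout treatment with a study drug", and the outline has the same figure. Exclusion criterion 2 (outline and Section 9.3) refers to "disorders of lipid metabolism characterized by hypertriglyceridemia (serum triglyceride concentration > 250 mg/dL". The titration rules for patients starting PN hold the drug, or remove the patient, at values above 250 mg/dL.

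The termination rules give no triglyceride figure of their own. The outline stops treatment when "TG or direct bilirubin levels remain above the defined limits (see above, Intravenous lipid dose management) after reduction of the dosage". Sections 6.1, 7.3 and 11.2.4 point to Section 10.3.4.

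There is a separate slip in Section 10.3.4, part A, for patients starting PN: "Once the target dose has been reached at level of serum TG ≤ 250 mg/mL, TG levels will be assessed monthly". The matching sentence in the outline has mg/dL.

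**The concern.** A confirmatory test should ask whether the value that raised the alarm has persisted, so it needs the limit used in the first test. As printed in the outline, it has a limit ten times lower, and the repeat no longer separates a transient rise from a persistent one. A patient whose triglycerides had returned well inside the permitted range would still meet the printed condition for dose reduction or removal.

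This sentence drives action in children who depend on parenteral lipid, and the termination rules lean on it. An unneeded removal also has a cost for the data. Early terminations are replaced "unless the decision to terminate was made for safety reasons (including intravenous lipid dose management"; Section 7.3 confirms that withdrawals for lipid dose management are not. Such a patient would not reach Day 90, although Section 7.2.1 defines the sample as patients who have completed Day 90, and would fall outside the per-protocol set of Section 7.2.2.

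**Working it through.** **Inputs as printed**

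| Place in the protocol | Use | Limit |
|---|---|---|
| Study outline, part B | First monthly test | 250 mg/dL |
| Study outline, part B | Seven-day confirmatory test | 250 mg/L |
| Section 10.3.4, part B | Seven-day confirmatory test | 250 mg/L, then (> 250 mg/dL) |
| Study outline and Section 10.3.4 | General limit on treatment | 250 mg/dL |
| Study outline and Section 9.3 | Exclusion criterion 2 | 250 mg/dL |
| Study outline and Section 10.3.4, part A | Hold or remove during titration | 250 mg/dL |
| Study outline, part A | Switch to monthly testing | 250 mg/dL |
| Section 10.3.4, part A | Switch to monthly testing | 250 mg/mL |

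**Confirmatory limit.** 1 L = 10 dL, so 250 mg/L ÷ 10 = 25 mg/dL. Ratio to the first-test limit: 250 ÷ 25 = 10. With the unit corrected, 250 mg/dL × 10 = 2,500 mg/L, and the ratio is 1.

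**Values affected.** Under the printed limit, a repeat value above 25 and up to 250 mg/dL counts as confirmed when it should not. For illustration, assume a repeat of 120 mg/dL, which is 1,200 mg/L. It exceeds 250 mg/L, so the printed rule calls for action. It does not exceed 250 mg/dL, so the intended rule calls for none.

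**Section 10.3.4, part B.** The sentence equates 250 mg/L with a value above 250 mg/dL. These differ tenfold and cannot both be the limit.

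**Cost of one unneeded removal before Day 91.** Section 7.2.1 plans 24 patients per arm within each age group. One unreplaced removal is 1 ÷ 24 = 4.2% of that cell. This is the arithmetic of a single removal. The documents give no basis for estimating how often it would happen.

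**Monthly-testing slip.** 250 mg/mL × 100 mL per dL = 25,000 mg/dL, and 25,000 ÷ 250 = 100 times too high. It concerns testing frequency only. It has little practical effect because the drug is held during titration at any value above 250 mg/dL.

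**The case against.** The strongest reply is that only one reading is workable. The preceding sentence sets 250 mg/dL, the word *still* points back to it, and the general text links removal to persistently high levels. The bilirubin rule uses one limit for both its tests. Section 10.3.4, to which most termination rules refer, prints the correct unit in brackets. Harm needs a chain of events: a first value above 250 mg/dL, a repeat between 25 and 250 mg/dL, a literal reading of the outline, a choice of removal over dose reduction, and all of this before Day 91. A removed patient stays in the ITT set and, if dosed and evaluated, in the safety set. The study has no primary outcome, power calculation or confirmatory test.

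Most of this stands. The intent can be recovered, the harm is conditional, and no comparison between arms is tilted. It does not make the text right. The outline carries the wrong unit with no correction, and Section 10.3.4 pairs the right unit with the wrong one. The Investigator's discretion can be read as covering only the choice between reducing the dose and removing the patient, so it is not a dependable safeguard. Section 11.4.1 itself asks for clearly defined units for laboratory data. A site that sensibly applies 250 mg/dL is departing from the outline as printed.

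**Conclusion.** The concern holds. The outline's confirmatory limit is wrong by a factor of ten, and Section 10.3.4 contradicts itself on the same limit. The practical impact is low but real: a risk of unneeded lipid reduction or removal if a site applies the printed figure, with 4.2% of an arm-by-age cell lost for each unreplaced removal before Day 91. No hypothesis test or sample size calculation is affected, and both blinded arms follow the same rule. The conclusion assumes that 250 mg/dL is intended, which the surrounding text supports throughout. It makes no claim about how often sites would misread the rule. It should be fixed because it is an action threshold in a pediatric safety rule and costs almost nothing to correct.

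**What to change.** Make three unit corrections at the next amendment:

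1. Study outline, serum triglycerides, part B: print the confirmatory limit as 250 mg/dL.
2. Section 10.3.4, part B: delete the mg/L figure so that only > 250 mg/dL remains.
3. Section 10.3.4, part A: print the limit for moving to monthly testing as 250 mg/dL.

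Send sites a short clarification that the confirmatory limit is 250 mg/dL. The protocol describes no eCRF check on this value; if an alert has been built, confirm that it uses 250 mg/dL. The cost is three edits and a short note, with no extra patients, visits or samples.

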**Duration of Treatment:**

Study treatment will last for a minimum of 90 consecutive days and as long as PN is indicated, up to 365 consecutive days. The study ends after the Final Study Visit, latest on Day 366 (see Section 1, Study Schedule). If the indication for PN continues after Study Day 365, PN will continue per normal institution policy. Study drugs will no longer be used.

Early termination of study treatment (Before Study Day 91)

The study treatment will stop if infusion of the study drug cannot be continued because TG or direct bilirubin levels remain above the defined limits (see above, Intravenous lipid dose management) after reduction of the dosage.

The study treatment will also be stopped if the Holman Index of a patient (biochemical marker for essential fatty acid deficiency (EFAD)) reaches or exceeds 0.4 or if any clinical symptoms of EFAD appear or when the patient's growth is inadequate (drop of 1 in z-score in a time period of 2 consecutive months).

The study treatment will also stop if enteral food tolerance increases and in consequence, less than 60% of the patient's

## Clinical Study Protocol SMOF-028-CP4 Smoflipid® (lipid injectable emulsion)

---

energy requirements are provided by PN for at least one month. If PN is still indicated after termination of the study treatment, it will continue per normal institution policy.

In case of early termination, patients will be replaced by randomizing additional patients unless the decision to terminate was made for safety reasons (including intravenous lipid dose management).

### Late termination of study treatment (Study Days 91 to 365)

After Study Day 90 the study treatment will be terminated as soon as nutritional needs can be fully covered from enteral or oral nutrition or PN is continued without a lipid emulsion (i.e., PN, or at least the lipid emulsion, is no longer indicated).

After Study Day 90 the study treatment will also stop if infusion of the study drug cannot be continued because TG or direct bilirubin levels remain above the defined limits (see above, Intravenous lipid dose management) after reduction of the dosage. In case of termination between Day 90 and Day 365, patients will not be replaced.

The study treatment will also be stopped if the Holman Index of a patient (biochemical marker for essential fatty acid deficiency (EFAD)) reaches or exceeds 0.4 or if any clinical symptoms of EFAD appear or when the patient's growth is considered inadequate (drop of 1 in z-score in a time period of 2 consecutive months).

The study is terminated on Day 366 at the latest, after the Final Study Visit (see Section 1, Study Schedule). If the indication for PN continues after study Day 365, study drugs will not be continued. PN will be prescribed per normal institution policy.

